THE EFFECT OF THERAPEUTIC TOUCH AND MUSIC REST ON SLEEPING APPLIED TO CHILDREN WITH LIVER TRANSPLANTATION

ID: TDK-2020-2358

NCT ID not yet assigned

Initial Release: 09/09/2021

MATERIAL AND METHOD

Desing of Research

The research was planned as a quasi-experimental study.

Place and Time of Research

The research will be carried out at İnönü University Turgut Özal Medical Center Liver Institute Pediatrics Clinic between February 2021 and October 2021. Pediatric transplant patients are followed in the 19-bed pediatric clinic of the institute.

Population and Sample of the Research

The population of the research will be children between the ages of 0-18 who had liver transplantation at İnönü University Turgut Özal Medical Center Liver Institute between February 2021 and October 2021 and were hospitalized in the pediatric clinic of the institute. The number of patients to be included in the study was calculated as 50 when the calculation was made by taking the confidence interval of 95% in the sample whose population is known. Of the 50 patients sampled, 24 will be included in therapeutic touch groups and 24 in music concert groups.

Randomization:

Assignment of the participants to the control and experimental groups will be done by stratification and block randomization method. Children will be stratified according to their age (0-1, 2-5, 6-12, 13-18 years) and randomization with blocks will be made. In order to prevent bias, children who were stratified were assigned to the control and experimental groups by drawing lots. The research groups will be written on separate papers and the group will be

determined by drawing lots during data collection. In this way, the number of children included in the groups and the probability of each child to be included in the study in the experimental or control group will be equalized.

Inclusion criteria:

*Being within a period of at least one month and at most two years after the transplant

* 0-18 years old

* Conscious

*spontaneous breathing

*No hearing problems

*Pain free

*Children who do not use sleeping pills will be included in the study.

Data Collection Tools

The data will be collected by face-to-face interview technique with the "Introductory Information Form", "Actigraphy" created by the researcher between February 2021 and October 2021.

Introductory Information Form

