The "Introductory Information Form", prepared by the researcher in line with the literature, consists of a total of 15 questions such as the age, gender, education status of the child and parent, and the time of transfer.

Actigraphy

Actigraphy measures the sleep and wake cycles of children and adolescents, detects motor activities with precision, is worn on wrists or ankles, and allows for recording and storing resting and activity patterns in a digital environment; small, lightweight, portable device in the form of a watch (Ertan & Alkan, 2012). The actigraphy device, which can be easily attached to the wrist of the patients, is used to evaluate and document the physical movements of the patients related to sleep. The device can keep a record of the patient's activity for 24 hours. The patient's information can be read and evaluated with the help of a special software of the device.

Data Collection

Data will be collected through face-to-face interviews with children aged 0-18 years, who had liver transplantation at İnönü University Turgut Özal Medical Center Liver Institute and were hospitalized in the pediatric clinic of the institute. The study will consist of therapeutic touch group and music groups. Which group the participants will be in will be determined by drawing lots. One of the experimental groups will be treated with therapeutic touch, and the other will be listened to a music preferred by the family/child. In both groups, children's sleep will be evaluated with pre-test, post-test and follow-up applications. In this study, applications to the "Therapeutic touch" and "music" groups will be done once a day (morning or afternoon) for three days, in the form of a 15-20 minute application period. Children's sleep will be evaluated with "Actigraphy" the day before the application, the day the application ends, and the fourth day after the application.

Intervention Materials

Therapeutic Touch:

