*Parents and children will be informed about "Therapeutic Touch", which is an easy-to-apply and non-invasive application before the procedure.

*One day before starting the "Therapeutic Touch" application, the child's sleep will be evaluated with "Actigraphy". Starting the day after the first measurement, "Therapeutic Touch" will be done in the form of a 20-minute daily application period for three days.

* Before the "Therapeutic Touch" application, the patient's room will be ventilated and a spacious and quiet environment will be provided during the application.

TD process:

*After the procedure was explained, the focus was on the child to be treated,

*Intended to help the child's treatment and sleep,

*The patient's energy field was scanned with the hands at a distance of 8-12 cm from the patient's skin (2 times)

*To remove the blockages determined regarding the energy flow and to facilitate the energy flow, manual cleaning was performed (2 times),

*Imbalances in the energy fields were tried to be treated by using mental visualization techniques such as dreaming, positive thinking and visualization, by directing the universal life energy to sick individuals with calm and rhythmic hand movements (2 times),

*Reassessed to determine whether success has been achieved in treating imbalances in the energy field.

Music Rest Group:

*Parents and children will be informed about the “Music Rest” before the procedure.

*One day before the “Music Rest” practice, the child's sleep will be evaluated with “Actigraphy”. Starting the day after the first measurement, the “Music Rest” will be held for three days as a 20-minute practice period per day. In order to help the child sleep, the child will be listened to music (such as lullaby, classical music) preferred by the patient or his family.

*Before the “Music Rest” application, the patient's room will be ventilated and a spacious and quiet environment will be provided during the application.

*The sound level of the music played will be kept between 45-65 dB.

*Nursing interventions will be written in more detail after the data of the research is collected.

Variables of the Study

Dependent variables: “Actigraphy”

Independent variables: Therapeutic touch, recital

Control variable: Age, gender, height, weight, place of residence, economic status, pain

Evaluation of Research Data

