IBM SPSS Statistics 25.0 package program will be used in the evaluation of the research data. Percentage, mean, standard deviation, normal distribution, t-test in independent groups, t-test and ANOVA tests in dependent groups, multiple linear regression and correlation analyzes will be used in the evaluation of the data. Statistical significance level will be accepted as $p<0.05$.

Ethical Principles of Research

Before the study, children and their parents will be included in the study after an explanation is given about the study and their written and verbal consents are obtained. Ethics committee approval was obtained from İnönü University Clinical Research Ethics Committee and institutional permission was obtained from İnönü University Turgut Özal Medical Center Liver Institute. It will be explained to the parents that not participating in the study will not have a negative effect on the treatment of their children.

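### The plan does not say where follow-up sleep is recorded, or how it is analysed, if a child leaves the ward before the eighth day

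*Protocol*

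**What the plan says.** The Protocol (Data Collection) sets three actigraphy recordings: "the day before the application, the day the application ends, and the fourth day after the application". Sessions "will be done once a day (morning or afternoon) for three days". Under Nursing Initiative, the descriptions of both groups fix when sessions begin: "Starting the day after the first measurement".

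The setting is the ward. Population and Sample of the Research describes children who "were hospitalized in the pediatric clinic of the institute", and before each session "the patient's room will be ventilated and a spacious and quiet environment will be provided during the application". The only time-related inclusion criterion is "Being within a period of at least one month and at most two years after the transplant". The other criteria concern age, consciousness, breathing, hearing, pain and sleeping pills.

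On the device, the Actigraphy section says it is portable and adds: "The device can keep a record of the patient's activity for 24 hours". It does not say where the child must be at each recording. The control variables (Variables of the Study) include place of residence, but not whether a given recording was made on the ward or at home.

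Evaluation of Research Data, in both the Protocol and the SAP, lists independent-groups t-tests, "t-test and ANOVA tests in dependent groups", regression and correlation. The Protocol names SPSS 25.0. The available text has no rule for early discharge, no missing-data rule and no dropout allowance.

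**The concern.** The follow-up is the only measurement taken after the sessions have stopped, so any statement about persistence rests on it. It comes several days after the last point at which the plan needs the child in the patient's room. The children are at least a month past transplant, conscious and pain free at entry, so discharge in that interval is possible.

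A child who has gone home is then either not measured or measured in a different bed, in a different environment. In the first case, follow-up describes only those still admitted. In the second, a change of sleeping place can look like persistence or loss of effect. Both arms are active, so the change from post-test to follow-up within each arm is likely to carry much of the interpretation, and drawing lots does not protect a within-arm change. Place of recording cannot be reliably reconstructed later if nobody writes it down.

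**Working it through.** **1. Length of the schedule.** Baseline is day 0. Sessions start the next day and run three days: days 1, 2 and 3. The post-test is on day 3. Follow-up, counted from the last session, is day 3 + 4 = day 7. Days 0 to 7 are 8 calendar days. Counting the fourth day from the first session gives day 1 + 4 = 5, or 6 calendar days. Reading it as study day 4 gives 5 calendar days. The eight-day count is the natural reading, but the wording does not force it.

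**2. What keeps the child on the ward to day 7.** Sessions in the patient's room imply presence to day 3, and so to the post-test. For days 4 to 7 no criterion, location or discharge rule appears.

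**3. Discharged children not measured.** The documents give no discharge rate, so the shares below are assumptions. The base is the 24 + 24 = 48 children allocated (the stated total of 50 does not equal this sum). Children left = 48 × (1 − share); standard-error factor = 1/√(1 − share).

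| Share gone before day 7 | Children left | Standard error |
|---|---|---|
| 10% | 43.2, about 43 | × 1.05 |
| 25% | 36 | × 1.15 |
| 40% | 28.8, about 29 | × 1.29 |

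The standardised difference detectable with 80% power at two-sided 0.05 is (1.960 + 0.842) × √(2/n), with n per arm: 0.81 at 24, 0.93 at 18 and 1.14 at 12.

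To link this to length of stay, suppose the remaining stay from baseline is exponential with median m days (illustration only). The share still admitted on day 7 is 0.5^(7/m): 50% for m = 7, 71% for m = 14 and 84% for m = 28, or about 12, 17 and 20 of 24 per arm. If every child stays to day 7, nothing is lost.

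**4. Discharged children measured at home.** Assume 25% are at home, and that home sleep differs from ward sleep by 30 or 60 minutes.

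- Within-arm change to follow-up: shift = 0.25 × 30 = 7.5 minutes, or 0.25 × 60 = 15 minutes, with no treatment effect at all.
- Between arms, with discharge unrelated to arm: the expected shift is zero. The chance imbalance in the proportion at home has standard deviation √(2 × 0.25 × 0.75/24) = 0.125, which is 3.75 or 7.5 minutes. This is mean-zero noise.
- Cost in precision: with an assumed within-setting standard deviation of 60 minutes and a 60-minute place difference, the variance is 3600 + 0.25 × 0.75 × 3600 = 4275. The standard error at 24 per arm goes from √(2 × 3600/24) = 17.3 to √(2 × 4275/24) = 18.9 minutes, about 9% more.

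**5. Which listed tests lose data when day 7 is missing.**

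- Paired t-test, pre-test to post-test: needs those two values only, so nothing is lost.
- Independent t-test at post-test: needs the post-test only, so nothing is lost.
- Three-wave repeated-measures ANOVA: the standard SPSS procedure deletes listwise, so the child's valid pre-test and post-test go too.

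**The case against.** The strongest reply is that nothing in the documents shows that children leave before day 7. There are no length-of-stay data and no stated reason for admission, and entry conditions such as being conscious and pain free do not establish readiness for discharge. That stands, and it rules out several stronger readings.

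- A reader might infer that follow-up must be either a selected remnant or a ward-home mix. A third outcome, nearly all children still on the ward, is not excluded.
- A reader might infer that those still admitted are the slower to recover. The documents do not say so.
- A reader might take the 7.5 minutes between arms in step 4 as bias. It is one standard deviation of a chance imbalance that can go either way, and an ordinary standard error already reflects it.
- A reader might infer that missing follow-up spoils every pre/post comparison. It affects only the three-wave ANOVA, provided each t-test is run on its own available data.

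It can also be said that lots drawn within age strata balance discharge between arms in expectation. That holds unless an intervention alters discharge. The Protocol's Music Rest section itself reports that music benefits hospital stay, so a difference by arm cannot be dismissed, but nothing shows that one will occur here.

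Finally, an expected-stay criterion would itself restrict the trial to longer-staying children, and a ward-only analysis conditions on something that happens after allocation. Both points are right and limit the remedy. They do not answer the missing place of recording or the missing analysis rule.

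**Conclusion.** The point holds in conditional form. On the natural reading, ward inpatients are followed for eight calendar days, and the available text neither ensures that they are still on the ward on day 7 nor says where discharged children are recorded. If a material share leaves earlier, the follow-up result is selected or mixes sleeping places. The main damage is to the within-arm change to follow-up (7.5 to 15 minutes under the step 4 assumptions) and to precision (standard errors up 5% to 29% for 10% to 40% unmeasured). Between-arm bias needs discharge to differ by arm. The post-test is largely unaffected, apart from the listwise loss in a three-wave ANOVA.

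The discharge shares, the home-ward differences and the 60-minute standard deviation are all assumptions; with no early discharge the effect is nil. Part of the SAP was not available, so absence is judged on the remaining text. The change is still worth making, because it is cheap and the place of recording is hard to recover afterwards.

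**What to change.** **Protocol, Data Collection.** State that follow-up actigraphy is done on the fourth day after the last session, wherever the child then is. Record ward or home for every recording.

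**Protocol and SAP, Evaluation of Research Data.** Replace the repeated-measures ANOVA with a linear mixed model (SPSS MIXED) that uses every child with any available measurement. Add recording place as a covariate in a sensitivity analysis. Show ward-only follow-up solely as a further sensitivity analysis, labelled as conditioning on a post-allocation event. The model keeps all pre-tests and post-tests, but it still assumes that missing follow-up is explained by the data observed.

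**Optional.** Add an entry condition, checked before the lot is drawn, that the child is expected to remain on the ward through follow-up. It reduces mixing, but it narrows the population and may slow recruitment. The document is dated 09/09/2021, late in a February to October 2021 window, so it may also reach few children.

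**Cost.** One data field, slightly more analysis work, and getting the device to and from any child already at home.

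### Time since transplant may span one month to two years and appears to be recorded, but it is not a control variable; the cost is modest chance imbalance and lost precision, not bias

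*Protocol*

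**What the plan says.** Under Inclusion criteria, the protocol takes children "Being within a period of at least one month and at most two years after the transplant". The same list requires that they be free of pain.

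Under Randomization, "Assignment of the participants to the control and experimental groups will be done by stratification and block randomization method", and the only stratification factor is age: "Children will be stratified according to their age (0-1, 2-5, 6-12, 13-18 years) and randomization with blocks will be made". Lots are drawn to decide the group. The planned arms are equal: "Of the 50 patients sampled, 24 will be included in therapeutic touch groups and 24 in music concert groups".

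The Introductory Information Form has 15 questions. The examples given are "the age, gender, education status of the child and parent, and the time of transfer". Time of transfer most naturally means time of transplant, because the Nursing Initiative section also describes the study children as having been transferred. That is an inference from context.

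Under Variables of the Study: "Control variable: Age, gender, height, weight, place of residence, economic status, pain". Time since transplant is not among the seven.

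The protocol and SAP sections on evaluation of data list independent and paired t-tests, ANOVA, multiple linear regression and correlation. Neither says which covariates enter the regression, whether pre-test sleep is used in the between-group comparison, or how the control variables are to be used.

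**The concern.** A child one month after a liver transplant and a child two years after it may sleep differently for reasons unrelated to touch or music. The plan pools them, does not stratify on time since transplant, and does not name it for adjustment, although the value seems to be on the form already. Pain is listed instead, and entry fixes it at none, so as a baseline covariate it can explain almost nothing.

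Two things are at stake in a trial of 48 children. The lots may by chance put more recently transplanted children in one arm, which would move the observed difference in sleep. And any variation in sleep that time since transplant explains stays in the error term, so the comparison is less precise than the collected data would allow.

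**Working it through.** **Inputs from the documents.** 24 children per arm; entry window 1 to 24 months; significance level 0.05 (two-sided assumed, as sidedness is not stated); allocation by lots within age strata.

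**Inputs assumed.** The documents give no effect size, SD or correlation. I take a true effect of 0.5 SD, a correlation r of 0.1, 0.3 or 0.5 between time since transplant and sleep, and, for figures in months, entry times spread evenly over the window.

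**The plan's own figure.** The sample size of 50 cannot be reproduced: the population size, expected proportion and margin of error are not given. The allocated total is 24 + 24 = 48, and the arm size of 24 is used below.

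**Step 1: chance imbalance.** The standard error of the standardised difference between arms is sqrt(1/24 + 1/24) = 0.289 SD. The chance of an imbalance above 0.25 SD is 39%, and above 0.5 SD it is 8%. An even spread over 1–24 months has SD 23/sqrt(12) = 6.64 months, so the 95% range for the difference in arm means is ±1.96 × 0.289 × 6.64 = ±3.8 months.

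**Step 2: effect on the sleep contrast.** A one-standard-error imbalance shifts the contrast by r × 0.289, and the 95% range is ±1.96 times that.

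| r | One-SE shift (outcome SD) | 95% range |
|---|---|---|
| 0.1 | 0.03 | ±0.06 |
| 0.3 | 0.09 | ±0.17 |
| 0.5 | 0.14 | ±0.28 |

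**Step 3: bias and error rate over repeated randomizations.** In 20,000 simulated trials with no true effect, the mean bias of the unadjusted comparison was +0.002 SD (r = 0.3) and −0.002 SD (r = 0.5). Unadjusted type I error was 5.0% and 4.8%; adjusted, it was 5.1% and 4.9%.

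**Step 4: precision.** Adjustment multiplies the residual SD by sqrt(1 − r²). By the normal approximation, power = Φ(0.5 / (0.289 × residual SD) − 1.96). Unadjusted: 0.5/0.289 − 1.96 = −0.23, so 41%.

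**Step 5: the same with pre-test sleep in the model.** Assume a pre/post correlation of 0.6 and that time since transplant correlates r with both. Pre-test alone leaves residual variance 1 − 0.36 = 0.64. The partial correlation of time since transplant with post-test sleep is then 0.4r / (sqrt(1 − r²) × 0.8) = 0.05, 0.16 and 0.29, so it removes a further 0.3%, 2.5% or 8.3% of the residual variance.

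| r | Time since transplant added to an unadjusted comparison | Time since transplant added to pre-test sleep |
|---|---|---|
| 0.1 | 41% → 41% | 58% → 58% |
| 0.3 | 41% → 44% | 58% → 59% |
| 0.5 | 41% → 52% | 58% → 62% |

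**Step 6: the entry window itself.** The Population and Sample section describes children transplanted at the centre between February and October 2021, with the research in the same months. Read literally, time since transplant could not exceed about nine months. An even spread over 1–9 months has SD 8/sqrt(12) = 2.3 months. If the relation with sleep is linear with the same slope per month, r = 0.3 over the full window becomes about 0.11, and r = 0.5 becomes about 0.20.

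**The case against.** The strongest answer is that lots are drawn. Randomization makes time since transplant independent of arm, the standard error of the comparison already allows for chance imbalance, and Step 3 confirms it. The same remark could be made about any unstratified prognostic variable in a trial of 48. This stands, and it limits the point to precision and protection against an unlucky draw. The protection has some value: if the imbalance in this one trial were 0.5 SD (8% chance), the simulated unadjusted false-positive rate is about 7% at r = 0.3 and 10% at r = 0.5. At a typical imbalance of 0.29 SD it stays near 5%.

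Second, every child has pre-test actigraphy, and time since transplant hardly changes over the study days, so baseline sleep would absorb much of its influence. This also stands (Step 5). But neither document says that the pre-test enters the between-group comparison, so the argument supports specifying both.

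Three stronger readings are tempting:

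- A reader might infer that recovery stage is confounded with treatment, especially as "The research was planned as a quasi-experimental study". The label is at odds with the procedure, but the procedure described is random allocation, and systematic confounding would require it to fail.
- A reader might infer that listing pain is a mistake or wastes a degree of freedom. Pain may be controlled by restriction, and it could vary after entry. A constant is collinear with the intercept and uses no further degree of freedom. The documents also never say that the control-variable list is the regression's covariate set.
- A reader might infer that time since transplant is the only recorded marker of recovery. Only examples of the form's 15 questions are given, so this cannot be verified.

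**Conclusion.** The point holds as a modest improvement in precision. A baseline variable that may range from 1 to 24 months, and is apparently collected, is used neither in stratification nor among the control variables. Neither the validity of the comparison nor its overall type I error is affected.

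The gain in power for a 0.5 SD effect runs from nothing at r = 0.1 to about 11 percentage points at r = 0.5 if nothing else is adjusted for. It is about 4 points at most over that range once pre-test sleep is in the model. These figures rest on assumed correlations, an assumed effect size and the reading of time of transfer as time of transplant. If the population wording means that transplants fall within the study months, the gain would probably be smaller still.

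Pain, fixed at none on entry, should not be relied on as a baseline covariate. The documents name no pain instrument or time of measurement, so its role needs to be stated.

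**What to change.** 1. Add time since transplant to the control variables under Variables of the Study, and confirm that the form's time of transfer is the transplant date.
2. In both sections on evaluation of data, state that the multiple linear regression comparing touch with music will include pre-test actigraphy, age stratum and time since transplant. Baseline sleep is likely to contribute most.
3. Tabulate time since transplant by arm at baseline.
4. Say whether pain is controlled by restriction at entry or measured later, and if measured, how and when.
5. Reconcile the one-month-to-two-year entry criterion with the population definition tied to February–October 2021.

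If the form records the transplant date, no new data are needed for items 1 to 3. Adding time since transplant costs one model degree of freedom: about 2% of the 46 that remain after fitting two arms to 48 children (1/46). If r is near 0.1 the change gains essentially nothing, but it loses little.

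### The dependent-groups ANOVA, run in SPSS in the standard way, drops any child missing one of three recordings, so it would describe different children from the listed t-tests, and no test is named as the main one

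*Protocol*

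**What the plan says.** **Recordings.** The Protocol's Data Collection section plans a pre-test, a post-test and a follow-up in both groups, with actigraphy on "the day before the application, the day the application ends, and the fourth day after the application". The Actigraphy section adds that "The device can keep a record of the patient's activity for 24 hours", so three separate recordings appear to be needed (an inference).

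**Arms.** The Population and Sample section gives a total of 50 and two arms of 24, which sum to 48.

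**Analysis.** The Protocol's Evaluation of Research Data section states that "IBM SPSS Statistics 25.0 package program will be used in the evaluation of the research data". It then lists tests, among them "t-test in independent groups" and "t-test and ANOVA tests in dependent groups". The SAP section of the same name repeats the list without the software. Neither text, as supplied, ties a test to an outcome, a time point or a main comparison. Neither mentions missing recordings, an analysis set, imputation or a mixed model.

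**The concern.** A repeated-measures ANOVA in its standard SPSS form needs one complete row per child. A child with valid pre-test and post-test recordings but no follow-up is removed from it entirely, although two of the three recordings are in hand. A paired t-test of pre-test against post-test would keep that child, and so would an independent-groups t-test at post-test. Three listed analyses of one outcome would then rest on three different sets of children, with nothing to say which result counts if they disagree.

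Two things are at stake. One is precision, which is already limited with 24 children per arm. The other is possible bias in the ANOVA results: if children who slept better at post-test were more likely to miss the follow-up, the completers would be a selected group even at post-test, where every child had been observed.

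**Working it through.** **Inputs from the documents:** 24 children per arm (48 in all); three recordings per child; the listed tests; SPSS 25.0. **Assumed, because the documents give no figure:** the missing rate, the within-child correlation, the size of the true difference and the missingness mechanism. The plan has no figure of its own on this point to reproduce.

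**1. Children kept by each analysis.** Let each recording be missing independently with probability m. The expected numbers are 48(1−m)³ with all three recordings, 48(1−m)² with pre-test and post-test, and 48(1−m) with a valid post-test.

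| m | ANOVA (all three) | Paired t-test, pre and post | Independent t-test at post-test | Valid post-test but not in ANOVA |
|---|---|---|---|---|
| 5% | 41.2 | 43.3 | 45.6 | 4.4 |
| 10% | 35.0 | 38.9 | 43.2 | 8.2 |
| 15% | 29.5 | 34.7 | 40.8 | 11.3 |

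If only the follow-up is missed, in 10%, 20% or 30% of children, the ANOVA keeps 43.2, 38.4 or 33.6, while all 48 have a post-test.

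**2. Precision when missingness is unrelated to sleep.** For the post-test difference, the standard error in completers relative to that in all children with a post-test is √[(1−m)/(1−m)³] = 1/(1−m). This gives 1.05, 1.11 and 1.18 for m = 5%, 10% and 15%.

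For power, take the difference that 24 per arm would detect with 80% power at two-sided 5%: (1.96 + 0.84)√(2/24) = 0.81 SD. With power = Φ(0.81√(n/2) − 1.96) and n per arm taken from the table, all valid post-tests against completers give 78% against 74%, 76% against 67%, and 73% against 59%.

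**3. Bias when missing follow-up depends on post-test sleep.** Simulated trials used 24 per arm, within-child correlation 0.4 or 0.6, and a true difference of 0.50 SD at post-test. Only the follow-up was missing, with a logistic probability rising with post-test sleep (slope 1.2 per SD).

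| Follow-up missing | Raw post-test difference, completers |
|---|---|
| 17% | 0.44 |
| 24% | 0.42 |
| 35% | 0.40 to 0.41 |

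- All post-test data return 0.50.
- The raw completer estimate is too small by (0.50 − 0.44)/0.50 = 12% to (0.50 − 0.40)/0.50 = 20%. Its standard error is 0.30 to 0.33, against 0.28 to 0.29 with all post-test data.
- An ANOVA with an arm factor would test arm by time, which is a contrast of changes. The pre-to-post change difference in completers is about 0.44 to 0.475. That is too small by (0.50 − 0.475)/0.50 = 5% to (0.50 − 0.44)/0.50 = 12%.

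**4. Sensitivity to the assumed slope.** With correlation 0.5 and about 20% to 26% missing, the raw completer difference is 0.50 at slope 0, 0.49 at slope 0.4 and 0.45 at slope 0.8. At slope 0 there is no bias.

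**The case against.** A reader might infer that a child with one missing recording disappears from the touch-versus-music comparison altogether, and that the comparison is therefore biased by 12% to 20%. The documents do not support that. The only test they name as between-group is the independent-groups t-test, which keeps every child with a valid recording at the time point tested. They give the ANOVA no arm factor and do not call it the main analysis. The 12% to 20% also describes a raw post-test difference, whereas an arm-by-time test would show about 5% to 12% under the same assumptions. Even the raw bias of 0.06 to 0.10 SD is about a third of its standard error or less.

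Three further objections are fair:

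- Neither document reports any missingness. The children are inpatients and the schedule lasts about a week, so a link between missing follow-up and sleep is conjecture.
- Deletion of incomplete children is a property of the standard procedure, not something the plan states. Part of the SAP was not available, so a rule there cannot be excluded.
- A stated missing-data rule with a post-test ANCOVA would also protect the post-test comparison.

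These objections limit the harm but do not remove the point. For a question spanning three recordings, the one suitable listed method discards valid data, and the supplied text neither overrides this nor says which of the differing results is to be believed.

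**Conclusion.** The point holds for the ANOVA and for the consistency of the listed analyses. It does not hold as a claim that the between-arm comparison as a whole loses these children or is biased.

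The loss follows directly from the three-recording design and the standard SPSS procedure; its size rests on an assumed missing rate. At 5% to 15% per recording, about 4 to 11 children with a valid post-test fall out of the ANOVA. If missingness is unrelated to sleep, precision is the only cost. Bias arises only if missing follow-up depends on sleep; at the strong dependence assumed here it is modest relative to the sampling error.

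Reading the ANOVA as covering all three days is natural but not explicit. The change is worth making because it is cheap and also settles which analysis is the main one.

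**What to change.** In the Evaluation of Research Data section of both the Protocol and the SAP, replace the dependent-groups ANOVA with text along these lines:

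*Sleep will be analysed with a linear mixed model (SPSS MIXED, Satterthwaite degrees of freedom). The three recordings are the responses. Fixed effects are arm, day and arm-by-day, with an unstructured within-child covariance. Every allocated child with at least one valid recording is included. The touch-minus-music differences at post-test and at follow-up, estimated from this model, are the main comparison.*

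Also report the number of valid recordings by arm and day, so that readers can see how much is missing.

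The cost is a wording change and slightly more analysis work in the software already named; no new data are needed. The limitation should be stated: the model is valid only if missingness depends on observed data alone, such as earlier recordings, and not on the unrecorded sleep itself.
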